#### Attachment 5: ECOG Performance Status Scale

Grade	ECOG Performance Status
0	Fully active, able to carry on all pre-disease performance without restriction
1	Restricted in physically strenuous activity but ambulatory and able to carry out work of a light or sedentary nature, eg, light house work, office work
2	Ambulatory and capable of all selfcare but unable to carry out any work activities. Up and about more than 50% of waking hours
3	Capable of only limited selfcare, confined to bed or chair more than 50% of waking hours
4	Completely disabled. Cannot carry on any selfcare. Totally confined to bed or chair
5	Dead

Source: Oken 1982

# Attachment 6: Prior Lines of Therapy for Multiple Myeloma

A line of therapy is defined as one or more cycles of a planned treatment program. This may consist of one or more planned cycles of single-agent therapy or combination therapy, as well as a sequence of treatments administered in a planned manner. For example, a planned treatment approach of induction therapy followed by autologous stem cell transplantation, followed by maintenance is considered one line of therapy. A new line of therapy starts when a planned course of therapy is modified to include other treatment agents (alone or in combination) as a result of disease progression, relapse, or toxicity. A new line of therapy also starts when a planned period of observation off therapy is interrupted by a need for additional treatment for the disease.

Source: Rajkumar 2015

# Attachment 7: Interpretation of Daratumumab Interference Reflex Assay (DIRA)

**Background**: Clinical response assessment in myeloma relies on serum protein electrophoresis (SPEP) and immunofixation electrophoresis (IFE). As daratumumab is a monoclonal IgG kappa antibody, the SPEP and IFE can be positive for daratumumab at the serum levels anticipated during this protocol for subjects who are randomly assigned to the daratumumab, lenalidomide, and dexamethasone group.

**Implementation:** To mitigate this interference, the Sponsor has developed the Daratumumab Interference Reflex Assay (DIRA) to distinguish a positive SPEP/IFE due to the presence of daratumumab versus the presence of the underlying (endogenous) monoclonal protein.a The DIRA test will be sent automatically to the central laboratory if a subject with IgG kappa multiple myeloma has an SPEP at or below 0.2 g/dL on 2 or more consecutive cycles. In addition, the DIRA test will be sent automatically to the central laboratory if a subject has an SPEP of zero, but persistently positive IFE for IgG kappa on 2 or more occasions.

#### **Interpretation of results:**

The results will be available to the investigator via the central laboratory interface and will be reported as either "POSITIVE" or "NEGATIVE".

POSITIVE: indicates that the sample is still *positive* for underlying (endogenous) monoclonal myeloma protein. Therefore, this patient is not in a complete response (CR), because the CR response criteria require a negative SPEP and serum IFE.

NEGATIVE: indicates that the sample is *negative* for underlying (endogenous) monoclonal myeloma protein. This subject may be in a CR if the other criteria for CR (including negative bone marrow aspiration/biopsy) are achieved.

<sup>a McCudden C, Axel A, Slaets D, et al. Assessing clinical response in multiple myeloma (MM) patients treated with monoclonal antibodies (mAbs): Validation of a daratumumab IFE reflex assay (DIRA) to distinguish malignant M-protein from therapeutic antibody. J Clin Oncol. 2015 (suppl; abstr 8590).

#### Attachment 8: ASTHMA Guidelines

Compone	anto of Coverity				1	Clas	sificatior	n of Asthma Seve					
Compone	ents of Severity		Intermitt	tent	N/	ild			sistent		Severe		
		0-4	5-11 yrs	12 + yrs	Mild 0-4 yrs 5-11 yrs 12 + yrs			Moderate 0-4 yrs 5-11 yrs 12 + y			1		12 + yrs
		yrs	j	, , -	,	- · · ) · ·	J.c	, , , , , , , , , , , , , , , , , , ,	- j -	, , ,	,,,,,,,,,,,,,,,,,,,,,,,,,,,,,,,,,,,,,,,	- , -	, , ,
	Symptoms		≤ 2 days/v	veek	≥ 2 days/wee	k but not d	aily	C	Daily		Throug	hout the day	,
	Nighttime awakenings	0 ≤ 2x/month		1-2x/ Month	3-4x/I	month	3-4x/ month	÷			> 1x/ month Often 7x/wee		
	symptom control (not prevention of EIB)		≤ 2 days/week but not daily and not more than 1x			E	Daily		Several time per day				
Impairment	Interference with normal activity		None		Minor limitation			Some	limitation		Extremely limited		
Normal FEV₁/FVC : 8-19 yr 85%	Lung function	N/A	Normal FEV 1 between exacerbations	Normal FEV1 between exacerbations	N/A			N/A			N/A	3	
20-39 yr 80% 40-59 yr 75%			> 80%	> 80%		> 80%	> 80%		60-80% 60-80%	IN/A	< 60%	< 60%	
60-80 yr 70%	FEV1/FVC		> 85%	Normal		> 80%	Normal		75-80%	Reduced 5%		< 75%	Reduced
Risk	Exacerbations requiring oral systemic corticosteroids	0-1/year		≥ 2 exacerbations in 6 months requiring oral steroids or >4 wheezing episodes/1 year lasting >1 day and risk factors for persistent asthma	≥ 2/year Relative annual risk may be related to FEV 1 .	≥ 2/year Relative annual risk may be related to FEV 1 .	
 
≥ 2 exacerbations in 6 months requiring oral steroids or >4 wheezing episodes/1 year lasting
 
>1 day and risk factors for persistent asthma
 
	≥ 2/year Relative annual risk may be related to FEV 1 .	≥ 2/year Relative annual risk may be related to FEV 1 .	≥ 2 exacerbations in 6 months requiring oral steroids or >4 wheezing episodes/1 year lasting >1 day and risk factors for persistent asthma	≥ 2/year Relative annual risk may be related to FEV 1 .	≥ 2/year Relative annual risk may be related to FEV 1 .	
			Consider	severity and i	nterval since last exa	cerbation.	Frequency	and severity may flu	uctuate ove	er time for p	atients in any seve	rity category	

Recommended Step for Initiating Treatment		Step 1	Step 2				Step 3 and short cours sterc	se of oral	Step 3: medium dose ICS and consider short course of oral steroids	Step 3 an consider short cours of oral steroids	short course	of oral n s IC a sh	Step 3: nedium dose S OR Step and consider nort course c oral steroids	4 consider short of course	
		0-4 years: If no clear ber	nefit is obs	served in			onsider a	alternate o	diagnosis or	adjusting	therapy. 5-1	1 and 12+ year	s: adjust t	herapy acc	ordingly.
Con	npone	nts of					Class	sificatio	on of As	sthma	Control				
	Ċontro				Well Cont				t Well C				1	Contro	
	1		0-4		5-11 yrs	12 + yrs		1 yrs	5-11 y	/rs 12	+ yrs	0-4 yrs	5-11	yrs 1	2 + yrs
		Symptoms	≤ 2 days/week but not more than once on each day ≤ 2 days/ week				> 2 days/week or ultiple times on ≤2 days/week > 2 days/ week				Throughout the day			у	
	Nighttime awakenings		≤ 1x/month			≤ 2x/month	> 1x/	'month	≥ 2x/mo	≥ 2x/month 1-3x/week		> 1x/week	≥ 2x/v	veek ≥	4x/week
	-	erference with ormal activity	None					Some limitation				Extremely limited			
Impairment		BA use for symptom rol (not prevention of EIB)	≤ 2 days/week				> 2 days/week					Several times per day			
	F	Lung function EV 1 or peak flow FEV1/FVC	N/	A	> 80% > 80%	> 80%	٢	N/A	60-80 75-80		-80%	N/A	< 60 < 75		< 60%
	Val	idated questionnaires ATAQ ACQ ACT				0 ≤ 0.75 ≥ 20					1-2 ≥ 1.5 6-19				3-4 N/A ≤ 15
	Exacerbations requiring				0-1/year					≥ 2/year					
Risk		oral systemic corticosteroids	Consider coverity and interval since last evenerhation							n					
		iction in lung growth/ gressive loss of lung function	Evaluation requires long-term follow-up												

Recommended Action for Treatment	
 
Maintain current step
 
Regular follow-up every 1-6 months
 
Consider step down if well controlled for at least 3 months
 
	Step up 1 step • Before step up: Review adherence to inhaler technique, an control. If alternative i used, discontinue it a treatment for that step • Reevaluate the lew control in 2-6 weel control. 0-4 years: If no clear in 4-6 weeks, consider a diagnoses or adjustin 5-11 years: Adjust the • For side effects, co alternative treatmer	d environmental treatment was and use preferred p. vel of asthma ks to achieve benefit is observed alternative g therapy. erapy accordingly. onsider	
 
Step up 1 step
 
Reevaluate in 2-6 weeks
 
For side effects, consider alternative treatment options
 
	Consider short course of oral steroids     Step up 1-2 steps     Before step up: Review adherence to medication, inhaler technique, and environmental control. If alternative treatment was used, discontinue it and use preferred treatment for that step.     Seevaluate the level of asthma control in 2-6 weeks to achieve control. 0-4 years: If no clear benefit is observed in 4-6 weeks, consider alternative diagnoses or adjusting therapy. 5-11 years: Adjust therapy accordingly.     For side effects, consider alternative treatment options.	
 
Consider short course of oral steroids
 
Step up 1-2 steps
 
Reevaluate in 2 weeks
 
For side effects, consider alternative treatment options
 

-------------------------------------	--	---	--	---	---	--

#### Attachment 9: Anticipated Events

#### **Anticipated Event**

An anticipated event is an adverse event (serious or non-serious) that commonly occurs as a consequence of the underlying disease or condition under investigation (disease related) or background regimen.

For the purposes of this study, the following events will be considered anticipated events:

- Anaemia
- Bleeding
- Bone diseases
- Hypercalcaemia
- Hyperuricemia
- Hyperviscosity syndrome
- Infection
- Neutropenia
- Renal failure or insufficiency
- Thrombocytopenia

Given the mechanism of action of JNJ-63723283, events associated with immune-mediated adverse events will also be considered as anticipated events, including:

- Pneumonitis
- Colitis
- Endocrinopathies (diabetes mellitus, pancreatitis, adrenal insufficiency, or hyperthyroidism)
- Hepatitis
- Transaminitis Grade  $\ge 2$  (AST or ALT > 3xULN and bilirubin > 2xULN, or AST/ALT > 10xULN)
- Systemic lupus erythematosus
- Neurologic: Guillain-Barré syndrome, myasthenia gravis/myasthenic syndrome, meningoencephalitis
- Nephritis
- Events suggestive of hypersensitivity, cytokine release, influenza-like illness, systemic inflammatory response syndrome, systemic immune activation, infusion-related reactions syndrome

Because this is the first study of the combination of JNJ-63723283 and daratumumab, other adverse events cannot be anticipated.

#### **Reporting of Anticipated Events**

All adverse events will be recorded in the CRF regardless of whether considered to be anticipated events and will be reported to the Sponsor as described in Section 12.3.1, All Adverse Events. Any anticipated event that meets serious adverse event criteria will be reported to the Sponsor as described in Section 12.3.2, Serious Adverse Events. These anticipated events are exempt from expedited reporting as

individual single cases to Health Authorities. However, if based on an aggregate review, it is determined that an anticipated event is possibly related to study drug, the Sponsor will report these events in an expedited manner.

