Overlapping toxicities of JNJ-63723283 and daratumumab are not expected based on nonclinical and clinical data generated to date with each compound. While infusion-related reactions (IRRs) are observed in approximately half of patients treated with daratumumab, IRRs occur in only approximately 3/17 (18%) subjects treated with JNJ-63723283. Given the mechanism of action of JNJ-63723283, events associated with immune-mediated adverse events will also be considered as anticipated events. Because this is the first study of JNJ-63723283 in combination with daratumumab, other unforeseen toxicities or adverse events cannot be anticipated. The potential risks of this drug combination will be mitigated by comprehensive and careful medical monitoring and pre- and postinfusion medications to reduce mAb-associated IRRs during the conduct of the study. The protocol is designed with a safety run-in phase and the safety will be closely monitored by an SET. In addition, the protocol and the Investigator's Brochures also provide appropriate preventative measures and guidelines for managing potential toxicities.

Immune-related risks have been identified with other anti-PD-1 antibodies, including gastrointestinal AEs such as colitis and diarrhea, pneumonitis, renal AEs such as nephritis and acute renal failure, hepatic AEs such as hepatitis and liver enzyme elevations, endocrinopathies such as hypothyroidism and adrenal insufficiency, and rash. A series of precautions has been put into place to manage the potential risks that could rise in response to JNJ-63723283 administration. In addition, safety of all participating subjects will be closely monitored via collaboration between the investigator and the Sponsor. Symptom monitoring and management guidelines are provided in the protocol.

The potential effect of coadministration of JNJ-63723283 and daratumumab on the incidence of anti-drug antibodies to either drug is unknown. Serum drug concentrations, anti-drug antibodies,

and safety will be monitored throughout the study. Pharmacokinetic-based drug-drug interactions resulting in clinically significant changes to exposure are not anticipated based on the nature of metabolism for protein therapeutics.

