# 3.2. Safety Evaluation

# **Dose-Limiting Toxicity (DLT) Evaluation - Safety Run-in**

Toxicities will be graded for severity according to the National Cancer Institute Common Terminology Criteria for Adverse Events (NCI-CTCAE), Version 4.03. During the 6-subject Safety Run-in phase, the DLT evaluation period is 28 days starting from the day of the first dose of study drug. Only toxicities that occur during the DLT evaluation period will be considered for DLT assessment. A subject who received  $\leq$ 75% of a planned dose without experiencing a DLT may be replaced.

Dose-limiting toxicity is defined as any of the events listed in Table 4. Toxicities with a clear alternative explanation (eg, due to disease progression) or transient toxicities ( $\leq$ 72 hours) and abnormal laboratory values without associated clinically significant signs or symptoms based on investigator determination can be deemed a non-DLT.

	e mining rowery	
DLT criteria for Non-hematologic Toxicity a		
AST or ALT	Grade $\geq$ 3 persisting $\geq$ 7 days after treatment with corticosteroids, Grade 4, or any case meeting Hy's Law criteria b	
Laboratory abnormality	Grade 3 persisting $\geq$ 7 days despite BSC c or Grade 4	
Any other	Grade 3 persisting $\geq$ 7 days despite BSC c or Grade 4; except Grade $\geq$ 3 asymptomatic or mildly symptomatic rash that can be adequately managed with supportive care or resolves to become asymptomatic or Grade $\leq$ 2 within 7 days of supportive therapy.	
Infusion-related reaction	Grade 4 infusion-related reaction that occurs during or within 24 hours after the infusion of JNJ-63723283 or daratumumab.	
DLT criteria for Hematologic	Toxicity a	
Neutropenia	Grade 4 neutropenia lasting more than 7 days despite BSC c , or Grade 3 febrile neutropenia (ANC <1000 cells/mm  and a single temperature >38.3°C or a sustained temperature >38°C for >1 hour), or sepsis	
Thrombocytopenia	Grade $\geq$ 3 thrombocytopenia with clinically significant bleeding and Grade 4 thrombocytopenia lasting more than 7 days despite BSC c	
Anemia	Grade 4 for more than 7 days despite BSC c	
DLT criteria for both Non-hematologic and Hematologic Toxicity a		
Any Grade 5 non-hematologic or hematologic event		

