#### Serious Adverse Event

A serious adverse event based on ICH and EU Guidelines on Pharmacovigilance for Medicinal Products for Human Use is any untoward medical occurrence that at any dose:

- Results in death
- Is life-threatening (The subject was at risk of death at the time of the event. It does not refer to an event that hypothetically might have caused death if it were more severe.)
- Requires inpatient hospitalization or prolongation of existing hospitalization
- Results in persistent or significant disability/incapacity
- Is a congenital anomaly/birth defect
- Is a suspected transmission of any infectious agent via a medicinal product
- Is Medically Important\*

\*Medical and scientific judgment should be exercised in deciding whether expedited reporting is also appropriate in other situations, such as important medical events that may not be immediately life threatening or result in death or hospitalization but may jeopardize the subject or may require intervention to prevent one of the other outcomes listed in the definition above. These should usually be considered serious.

If a serious and unexpected adverse event occurs for which there is evidence suggesting a causal relationship between the study drug and the event (eg, death from anaphylaxis), the event must be reported as a serious and unexpected suspected adverse reaction even if it is a component of the study endpoint (eg, all-cause mortality).

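### Attachment 9 exempts the study drug's own immune-mediated events from single-case expedited reporting to Health Authorities, against its own definition and, for serious unlisted suspected reactions, against Section 12.1.1

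*Protocol*

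**What the plan says.** Attachment 9 of the protocol opens with a definition. An anticipated event is one that "commonly occurs as a consequence of the underlying disease or condition under investigation (disease related) or background regimen". Ten disease-related entries follow, such as anaemia, infection and hypercalcaemia. A second list is then introduced on a different ground: "Given the mechanism of action of JNJ-63723283, events associated with immune-mediated adverse events will also be considered as anticipated events, including" pneumonitis, colitis, endocrinopathies, hepatitis, transaminitis, lupus, neurologic events (Guillain-Barré syndrome among them), nephritis, and a last entry covering hypersensitivity, cytokine release and infusion reactions. That makes nine entries. Section 1.4 repeats the classification: "events associated with immune-mediated adverse events will also be considered as anticipated events".

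Under Reporting of Anticipated Events, Attachment 9 states the exemption: "These anticipated events are exempt from expedited reporting as" "individual single cases to Health Authorities". It ends only when an aggregate review judges the event possibly related to study drug. How often that review takes place, and what triggers it, is left to a separate Anticipated Events Safety Monitoring Plan. Section 12.3.1 refers the recording and reporting of anticipated events to Attachment 9.

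Section 12.1.1 has its own rule. Where an event is serious and unexpected and there is evidence of a causal link to study drug, "the event must be reported as a serious and unexpected suspected adverse reaction". The same section settles expectedness by the Reference Safety Information in the Investigator's Brochures.

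**The concern.** An exemption of this kind suits events that the disease produces anyway, because a single case then says little about the drug. The second list is there for the opposite reason: the events follow from how the investigational drug works. A single serious case of that sort can be informative, and Attachment 9 describes this as the first study of the combination.

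At stake is which rule the Sponsor's safety group follows when the two sections disagree. Someone applying Attachment 9 literally could hold back a single-case report that Section 12.1.1 requires. In Parts 1 and 2 the Safety Evaluation Team is chaired by the Sponsor, and Section 3.2 foresees an IDMC only for Part 3. The Health Authorities are therefore an external recipient whose access to single cases matters.

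**Working it through.** No arithmetic applies. The check sets the passages against each other.

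1. **Definition against list.** The definition has two limbs, disease and background regimen. JNJ-63723283 is the agent being tested and falls under neither. The definition also requires that the event be common, yet Section 6.2.4.6 describes neurological events as uncommon with anti-PD-1 therapy, and Guillain-Barré syndrome is on the list. One entry is arguable: hypersensitivity and infusion reactions could partly fit background regimen if daratumumab is read that way, since Section 1.4 gives infusion reactions in about half of daratumumab-treated patients. The other eight entries do not fit.

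2. **Scope of the exemption.** It covers all anticipated events without separating the two lists, and has no carve-out for unexpected or causally suspected cases. It concerns one route only, as the table shows.

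| Reporting or review route | Where | Affected by the exemption? |
|---|---|---|
| Site to Sponsor, serious events, within 24 hours | 12.3.2, kept by Attachment 9 | No |
| Sponsor's own relatedness judgement on each serious anticipated event | 12.3.1 | No |
| SUSARs to investigators, and from there to the IEC/IRB | 12.3.1 | No |
| Safety Evaluation Team review, Parts 1 and 2 | 3.2 | No |
| Narrative safety report to investigators on serious anticipated events | 12.3.1 | Already tied to accumulating data |
| Expedited single case to Health Authorities | Attachment 9 | Yes |

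3. **When Section 12.1.1 is engaged.** Three conditions must hold together: serious, unexpected, and evidence of causality. The section makes no exception for anticipated events. Being named in Attachment 9 does not make an event expected; only the Reference Safety Information does, and it is judged on nature or severity.
   - If the event is not serious, not causally suspected, or listed: no conflict with Section 12.1.1.
   - If it is serious, suspected and unlisted: Section 12.1.1 requires the report and Attachment 9 exempts it. The two rules collide.

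4. **How many entries fall in the second group.** The Investigator's Brochure is not among the documents, so the answer lies between 0 and 9. The protocol gives hints both ways. Section 1.2.2 calls rash and pneumonitis expected, so pneumonitis may well be listed. Section 9.4.1, however, says cytokine release syndrome is not a recognised risk of PD-1 inhibitors or daratumumab, yet cytokine release is on the exempt list. The serious events named in Section 1.2.2, from 17 subjects, include no lupus, Guillain-Barré syndrome, myasthenia, meningoencephalitis, colitis or nephritis. None of this settles what the Reference Safety Information lists.

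5. **Internal logic.** The exemption ends when aggregate data show possible relatedness, but the mechanism of the drug is the stated reason for listing these events. Section 6.2.4 recommends attributing an inflammatory event to an immune cause, case by case, when no clear alternative is found. Section 12.3.1 has the Sponsor judge relatedness singly. The Sponsor could hold a positive single-case judgement while Attachment 9 says no expedited report is due.

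**The case against.** The best reply is that the exemption is narrow and deliberate. It names one recipient and leaves every other route in the table intact. The second list is an openly stated extension, repeated in Section 1.4, so it is not a slip. The clash with Section 12.1.1 depends on a document that is not available, and some entries are probably already listed. All of these limits stand. They do not remove the collision: a deliberate extension still leaves two incompatible rules for a serious, unlisted, suspected reaction, and nothing says which prevails.

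A reader might infer more than this, and the documents do not support it:

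- **That serious immune-mediated events go unreported.** They reach the Sponsor within 24 hours, and SUSARs go to investigators. Only the expedited single case to Health Authorities is exempted.
- **That the early safety signal in Parts 1 and 2 is lost.** The Safety Evaluation Team reviews treatment-emergent events as they arise and includes the enrolling investigators. Two or more DLTs halt new run-in enrollment (Section 3.1), and an excess of Grade 3 or higher immune-related events is a named ground for termination (Section 10.2). None of this depends on reports to Health Authorities.
- **That the transaminitis entry contradicts Table 4, where "any case meeting Hy's Law criteria" is a DLT.** The two overlap but serve different purposes. A case can be a DLT and also fall under Attachment 9, and as a DLT it reaches the team regardless.
- **That some number of cases would accrue before a report.** The trigger is a judgement of possible relatedness, and its threshold sits in the separate monitoring plan. No such count can be derived.

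**Conclusion.** The inconsistency is real, and its size can be stated only in part. Attachment 9 departs from its own definition for at least eight of its nine immune-mediated entries. It contradicts Section 12.1.1 for any of them that is serious, unlisted and causally suspected; the number of entries where that can arise is unknown, from none to all nine. The consequence is limited to expedited single-case reporting to Health Authorities.

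The practical reach is smaller since Amendment 2. Enrollment closed on 25 May 2018, combination treatment is discontinued, and Part 3 no longer applies. The text still matters: related serious events continue to be collected, including beyond the End-of-Treatment Visit (Sections 9.1.4 and 12.3.1.1), and Attachment 9 stands without a carve-out. This is a wording correction that should be made because it bears on safety reporting. It does not undermine the trial's safety oversight as a whole. The conclusion assumes that neither the Reference Safety Information nor the separate monitoring plan already resolves the point.

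**What to change.** Make one of two changes to Attachment 9. Either limit the exemption to the disease- or background-related list and put the immune-mediated events under a separate heading without it, or add a sentence saying that any event meeting the Section 12.1.1 condition is reported to Health Authorities as an expedited single case whether or not Attachment 9 names it.

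Then align two places in the body: the sentence in Section 1.4 that classes immune-mediated events as anticipated, and the sentence in Section 12.3.1 that hands reporting to Attachment 9. The separate monitoring plan should be checked for the same limit.

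The cost is protocol wording and a few more single-case reports. Treatment, data collection and analysis are unaffected.
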